4.3.2. Single Dose Pharmacokinetics (part A)

4.3.2.1. Endpoints/Variables

AUC (0- ∞), AUC (0-t), Cmax, tmax, $t_{1/2}$, F following single oral doses of GSK3915393.

AUC (0- ∞), AUC (0-t), Cmax, tmax, $t_{1/2}$, CL, V_d following IV dose of GSK3915393.

4.3.2.2. Main Analytical Approach

All pharmacokinetic parameters will be summarised. Full details will be provided in the OPS. Dose normalised AUC (0- ∞) [or AUC(0-t) if AUC (0- ∞) cannot be derived] and Cmax will be displayed graphically versus dose to provide a visual assessment of dose linearity.

4.3.3. Repeat Dose Pharmacokinetics (part B)

4.3.3.1. Endpoints/Variables

Assessment of the pharmacokinetics upon repeat dosing will be based on AUC(0-t), Cmax and tmax following 1st and 2nd dose, trough concentrations, $t_{1/2}$ (day 1 only, if data permit), Cmax accumulation ratio and Ro.

In addition to the PK sampling schedule outlined in the protocol a pre dose sample would be collected pre dose on days 4, 6, 8, 9, 10, 11, 12 and 13 in cohorts 2 and 3 of part B.

4.3.3.2. Main Analytical Approach

- a. All pharmacokinetic parameters will be summarised by time and dose. Full details will be provided in the OPS.
- b. Dose normalised AUC(0- τ) and Cmax after 1st and 2nd doses will be assessed descriptively.
- c. Log_e transformed AUC (0- τ) for the first dose on Days 1 and 7 will be analysed by a mixed effect model with dose, day (Day 1 and 7) and dose-by-day interaction fitted as fixed effects and participant as a random effect. The Kenward & Roger (KR) degrees of freedom approach will be used. The difference between the least square means for day 7 and day 1 at each dose and associated 90% CI will be exponentially back transformed to obtain point and 90% CI estimates for Ro for each active dose. Distributional assumptions underlying the model used for analysis will be examined by obtaining a normal probability plot of the residuals and a plot of the residuals versus the fitted values.
- d. Log_e transformed Cmax for the first dose on Days 1 and 7 will be analysed by a mixed effect model with dose, day (Day 1 and 7) and dose-by-day interaction fitted as fixed effects and participant as a random effect. The Kenward & Roger (KR) degrees of freedom approach will be used. The difference between the least square means for the day 7 and day 1 at each dose and associated 90% CI will be exponentially back transformed to obtain point and 90% CI estimates for Cmax accumulation ratio for each active dose. Distributional assumptions underlying the model used for analysis will be examined by obtaining a normal probability plot of the residuals and a plot of the residuals versus the fitted values.
- e. A preliminary assessment of time to achieve steady state will be made based on visual inspection, of pre dose concentrations plotted by day for each dose in order to determine the time points (days) to be included in the statistical analysis described in f.
- f. A mixed effects model will be fitted to log_e transformed pre dose concentrations with day (continuous variable) as fixed effects and participant as a random effect for each dose separately. The KR degrees of freedom approach will be used. The coefficient for the slope of the day effect on the loge-scale will be used to evaluate steady state for each dose. The 90% CIs for the slope for each dose will be calculated. Estimates should be exponentially back transformed to be presented. A slope of 1 indicates steady state. If individual dose levels are inconclusive on steady state, combined dose analysis would be considered. Distributional assumptions underlying the model used

for analysis will be examined by obtaining a normal probability plot of the residuals and a plot of the residuals versus the fitted values.

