AUC (0-10)	Area under the concentration-time dosing interval curve following 1 st dose from time zero to 10 hours post-dose
AUC (10-24)	Area under the concentration-time dosing interval curve following 2 nd dose from 10 hours to 24 hours post-dose.
AUC (0-24)	Area under the concentration-time curve from time zero to 24 hours post-dose.
Cmax 1 st dose	Maximum observed concentration following 1 st dose (0-10h), determined directly from the concentration-time data.
Cmax 2 nd dose	Maximum observed concentration following 2 nd dose (10-24h), determined directly from the concentration-time data.
tmax 1 st dose	Time to reach Cmax following 1 st dose (0-10h), determined directly from the concentration-time data.
tmax 2 nd dose	Time to reach Cmax following 2 nd dose (10-24h), determined directly from the concentration-time data.
Ctrough	Pre-dose concentrations on days 1-14 (days 2 3,5,7 and 14 in cohort 1*)
t _{1/2}	Apparent terminal half-life will be calculated as: $t_{1/2} = \frac{\ln 2}{\lambda_z}$
Cmax accumulation	Cmax accumulation will be calculated as Cmax 1 st Dose _{D7} /Cmax 1 st Dose _{D1}
Ro	Observed accumulations ratio will be calculated as AUC (0-10) _{D7} / AUC(0-10) _{D1}
Part C (CYP3A4 victim assessment)	
Cmax	Maximum observed concentration, determined directly from the concentration-time data.
tmax	Time to reach Cmax, determined directly from the concentration-time data.
AUC(0-t)	Area under the concentration-time curve from time zero to the time of the last quantifiable concentration (C(t)) will be calculated using the linear trapezoidal rule for each incremental trapezoid and the loge trapezoidal rule for each decremental trapezoid.
AUC (0-∞)	Area under the concentration-time curve extrapolated to infinity will be calculated as: $AUC(0 - \infty) = AUC(0 - t) + \frac{C(t)}{\lambda_z}$
t _{1/2}	Apparent terminal half-life will be calculated as:

Parameter	Parameter Description
	$t_{1/2} = \frac{\ln 2}{\lambda_z}$
F_G^1	$F_G = \text{AUC}_{H2O} \div \text{AUC}_{GFJ}$ (oral administration of GSK3915393)
F	Absolute bioavailability calculated as $[\text{AUC}(0-\infty)_{po}/\text{dose}_{po}] / [\text{AUC}(0-\infty)_{iv}/\text{dose}_{iv}]$

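### The 90% CI for the Part B trough slope is valid only if all participants share one slope and daily residuals are independent; SAP item f should add a random day slope

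*SAP*

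**What the plan says.** SAP 4.3.3.2 item f fits a mixed model to log-transformed troughs "with day (continuous variable) as fixed effects and participant as a random effect for each dose separately". It continues: "The KR degrees of freedom approach will be used" and "The 90% CIs for the slope for each dose will be calculated". After back-transformation, "A slope of 1 indicates steady state". No random day slope, residual covariance structure or fallback is named. The listed diagnostics are a normal plot and residuals against fitted values.

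The length of the series differs by cohort. SAP 4.3.1, Table 3 lists "Pre-dose concentrations on days 1-14 (days 2 3,5,7 and 14 in cohort 1", that is, five post-dose troughs in cohort 1. SAP 4.3.3.1 adds samples "pre dose on days 4, 6, 8, 9, 10, 11, 12 and 13 in cohorts 2 and 3 of part B". Together with days 2, 3, 5, 7 and 14, this gives 13 post-dose troughs (days 2 to 14) in cohorts 2 and 3. Thirteen is a maximum, because item e inspects the plots "in order to determine the time points (days) to be included in the statistical analysis described in f".

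SAP 1.1.2, Table 2 makes the point estimate and 90% CI for the day effect the planned summary for this secondary objective, beside descriptive statistics. By contrast, the food-effect model in SAP 4.3.4.2, with three days per participant, names unstructured R and G matrices and an ordered fallback.

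**The concern.** A random intercept removes differences in level between participants. It does not allow their trends to differ, and it treats residuals one day apart as no more alike than residuals 12 days apart. If participants' slopes differ, the replication that matters for the mean slope is 9 participants, yet the model works with about 107 residual df. Kenward-Roger adjusts the standard error and df within the covariance model it is given; it cannot supply a missing variance component. The planned residual plots are not designed to show differing slopes or serial correlation.

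Differing trends are plausible here. The protocol (2.3.1) describes the compound as a CYP3A4 substrate that in vitro is also a weak CYP3A4 inducer and a metabolism-dependent inhibitor, and 8.4.6 collects 4β-hydroxycholesterol to look for a change in CYP3A4 activity by Day 14. Such effects develop over time and may differ between people.

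At stake is the reported precision of the drift estimate. An interval that is too narrow excludes 1 too often when the mean slope is flat. It can also make a dose look conclusive when it is not; item f turns to a combined-dose analysis only if single doses are inconclusive, a term it does not define.

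**Working it through.** **Inputs from the documents**
- 9 active participants per dose (protocol 4.1.2, Part B).
- Trough days 2 to 14 (cohorts 2 and 3), or 2, 3, 5, 7 and 14 (cohort 1).
- 90% two-sided interval (SAP 4.3.3.2 f).

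**Assumptions**
- Log SD of troughs: sqrt(ln(1 + 0.35²)) = 0.340. This borrows the 35% within-subject CV that the plan states for Part C AUC and Cmax; no trough variance is given.
- Slope SD 0.01 to 0.03 per day; lag-1 (AR(1)) correlation 0.1 to 0.5. Neither is in the documents.
- Complete, balanced data.

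The plan gives no standard error or precision for this slope, so the only figure to reproduce is the nominal 90%.

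**Interval under item f.** With balanced data the random-intercept slope is the pooled within-participant slope:

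SE = s / sqrt(n × Sxx), df = n(m − 1) − 1

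- 13 troughs: Sxx = 182, df = 9 × 12 − 1 = 107, t = 1.659.
- 5 troughs: Sxx = 90.8, df = 9 × 4 − 1 = 35, t = 1.690.

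With one slope and independent residuals, SE = 0.340 / sqrt(9 × 182) = 0.0084 and the half-width is 1.659 × 0.0084 = 0.0139, about 1.4% per day. Simulated coverage is 90%, so the nominal level is reproduced.

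**Worked example: slope SD 0.02, 13 troughs**
- True variance of the estimated mean slope: (0.02² + 0.1156/182) / 9 = (0.000400 + 0.000635) / 9 = 0.000115; SD 0.0107.
- Residual variance as the model sees it: 0.1156 + 8 × 182 × 0.02² / 107 = 0.1156 + 0.0054 = 0.1210.
- Model SE: sqrt(0.1210 / (9 × 182)) = 0.0086.
- Ratio of true SD to SE: 0.0107 / 0.0086 = 1.25.
- Approximate coverage: 2Φ(1.659 / 1.25) − 1 = about 82%; simulation gives 81% to 82%.

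**Simulated coverage of the nominal 90% CI** (at least 20,000 cohorts per scenario, true mean slope zero; repeat runs differ by less than one point)

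| Scenario | 13 troughs | 5 troughs |
|---|---|---|
| Common slope, independent residuals | 90% | 90% |
| Slope SD 0.01 per day | 88% | 89% |
| Slope SD 0.02 per day | 81% | 86% |
| Slope SD 0.03 per day | 74% | 83% |
| Lag-1 correlation 0.1 | 87% | 89% |
| Lag-1 correlation 0.3 | 80% | 87% |
| Lag-1 correlation 0.5 | 70% | 84% |

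The result also depends on the assumed log SD. At slope SD 0.02 with 13 troughs, coverage is 71% if the log SD is 0.20 and 86% if it is 0.50.

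**Interval after the change.** The mean of the nine participant slopes, with SE = SD(slopes)/sqrt(9) and t on 8 df (1.860), covers 90% in every row for both sampling schedules. With 13 troughs the mean half-width goes from about 1.4% to 1.5% per day with no violation, from 1.4% to 2.0% at slope SD 0.02, and from 1.3% to 1.9% at lag-1 correlation 0.3.

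**The case against.** A reader might infer that the interval simply is too narrow. The documents do not support that: with a common slope and independent residuals, about 107 df is right and coverage is 90%. Every shortfall above rests on an assumed slope SD or correlation. This stands, and the point is conditional.

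Drug carry-over is a poor reason to expect serial correlation. The half-life is predicted to be under 2 h, so after the 14 h overnight interval less than 2^-7 = 0.8% remains. This stands too; participant-specific trends or slow day-to-day drift are the better argument. The protocol's modelling also predicts modest CYP3A4 effects on a sensitive substrate (less than a 1.6-fold change in AUC from inhibition, up to 160 mg BID). That makes large slope spread less likely but does not rule out differing trends.

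It is also tempting to conclude that steady state will be misjudged because this interval decides it. The documents do not say so. No formal hypothesis is tested, item f gives no rule that a CI excluding 1 rejects steady state, protocol 9.4.2 relies on visual inspection, and the SAP estimates accumulation ratios separately. Moreover, at slope SD 0.03 a participant one SD from the mean drifts exp(0.03 × 12) = 1.43-fold over 12 days. Those scenarios describe under-coverage for the mean slope, not a cohort in which everyone is at steady state.

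Finally, a bounded random-slope fit may estimate the slope variance at zero; with 13 troughs and no true spread this happens in about 56% of cohorts. A fit that then reverts to the SAP model still covers 90% to 93% in the scenarios checked, so this does not defeat the remedy, but the fallback should name the case.

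**Conclusion.** The point holds in conditional form. Item f gives a valid 90% CI only under a common slope and independent daily residuals, and the SAP neither justifies these assumptions nor says what happens if they fail. Under moderate departures, coverage with 13 troughs falls to roughly 70% to 88%; with cohort 1's five troughs, to roughly 83% to 89%. The longer sampling in cohorts 2 and 3 therefore increases the exposure, unless item e drops days. These sizes rest on an assumed log SD of 0.34, complete data, and slope variances and correlations that the documents do not give. Severity is low: one secondary objective in a Phase 1 study, estimation only, with plots alongside. It is worth changing because the better method is cheap.

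**What to change.** In SAP 4.3.3.2 item f, specify a random intercept and a random day slope for participant. Add: if the model does not converge, or the slope variance is estimated at zero, use the mean of the per-participant slopes with a t interval on n-1 df, where n is the number of active participants in the analysis.

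The cost is one SAP sentence and, when the simpler model is true, a slightly wider interval: t of 1.86 on 8 df against 1.66 on 107 df, and a mean half-width of about 1.5% against 1.4% per day with 13 troughs. No extra samples or participants are needed.

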4.3.4. Assessment of Food Effect (Part B)

4.3.4.1. Endpoints/Variables

Food effect assessments will be based on AUC (0- τ), Cmax and tmax after 1st dose.

4.3.4.2. Main Analytical Approach

For each dose level separately, Log_e-transformed AUC(0- τ) and Cmax after 1st dose (on days 3, 5 and 7) will be statistically analysed using a Mixed effects model with:

- Prandial state ~ (high fat (day 5 data), standard meal (day 7 data) or fasted (day 3 data))
- participant as random effect

The Kenward and Roger method for approximating the denominator degrees of freedom and correcting for bias in the estimated variance-covariance of the fixed effects will be used. An unstructured type of the covariance matrices R (accounting for the within participant variability) and G (accounting for the between participant variability) will be used.

The estimated geometric mean ratios and 90% CI for (high fat meal: fasted) and (standard meal: fasted) will be derived for each dose (i.e., Low dose, Medium dose and High dose).

Distributional assumptions underlying the model used for analysis will be examined by obtaining a normal probability plot of the residuals and a plot of the residuals versus the fitted values (i.e. checking the normality assumption and constant variance assumption of the model respectively) to gain confidence that the model assumptions are reasonable. If there are any departures from the distributional assumptions, alternative transformations, such as data squared or square root of data, will be explored. Non-parametric analyses will be conducted if the normality assumption does not hold for any of the alternative transformations. If this model fails to converge, alternative covariance structures may be considered in the following order (1) Compound Symmetry (CS) and (2) Variance Components (VC).

tmax after 1st dose on day 3 and day 5 will be analysed non parametrically applying a Wilcoxon signed rank test and a point estimate and distribution free 90% CI for the median difference in tmax for (high fat meal vs fasted) will be derived by specifying the CIQUANTDF option in SAS Proc Univariate. The analysis will be repeated for tmax after 1st dose on days 3 and day 7 to derive point estimate and distribution free 90% CI for the median difference of (standard meal vs fasted).

4.3.5. CYP3A4 victim assessment – Impact of Grapefruit Juice (Part C)**4.3.5.1. Endpoints/Variables**

AUC (0-∞) [or AUC (0-t) or AUC (0-τ)], Cmax following single oral doses of GSK3915393 with water or with GFJ.

4.3.5.2. Main Analytical Approach

Log transformed AUC (0-∞) [or if not available AUC(0-t) or AUC (0-τ)] for periods 3 and 4 will be analysed utilising a mixed model with fixed regimen and period effects and random subject effect. Between regimen differences will be computed and back transformed to provide point estimate and 90% CI for the ratio of AUC for GSK3915393 PO with GFJ: GSK3915393 PO + water, and an estimate of F_G defined as the ratio of AUC GSK3915393 PO with water: GSK3915393 PO + GFJ. Distributional assumptions underlying the model used for analysis will be examined by obtaining a normal probability plot of the residuals and a plot of the residuals versus the fitted values.

Similar analysis will be conducted for log transformed Cmax to provide an estimate of the ratio of Cmax for GSK3915393 PO with GFJ: GSK3915393 PO + water.

In addition, descriptive summaries of AUC and Cmax will be produced for each regimen.

4.3.6. CYP3A4 victim assessment – impact of itraconazole (part C)**4.3.6.1. Endpoints/Variables**

AUC (0-∞) [or AUC (0-t) or AUC (0-τ)], Cmax following single IV / oral doses of GSK3915393 alone/with water or with ITZ.

4.3.6.2. Main Analytical Approach

Log transformed AUC (0-∞) [or if not available AUC(0-t) or AUC (0-τ)] will be analysed for periods 1 and 2 utilising a mixed model with regimen fixed effect and subject random effect. Between regimen differences will be computed and back transformed to provide point estimates and 90% CI for the ratios of AUC for GSK3915393 IV + ITZ: GSK3915393 IV. Distributional assumptions underlying the model used for analysis will be examined by obtaining a normal probability plot of the residuals and a plot of the residuals versus the fitted values.

A similar mixed model analysis utilizing period 3-5 data will be conducted to provide point estimates and 90% CI for ratio of AUC for GSK3915393 PO + ITZ: GSK3915393 PO + water. These analyses will also be conducted for log transformed Cmax to derive point estimates and 90% CI for the Cmax ratios of interest.

In addition, descriptive summaries of AUC and Cmax will be produced for each regimen.

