### Statistical Analyses of Pharmacokinetic Data

Dose linearity (Part A): Single dose linearity will be assessed by visual inspection of dose normalised AUC (0-∞) [or if not available AUC(0-t) or AUC (0-t')] and Cmax values versus dose. Analysis of loge-transformed parameters may be carried out, using the power model.

Food effect (Part B): The ratio of fed state to fasted state will be assessed for parameters Cmax and AUC (0-T) after 1st dose.

Repeat vs Single dose (Part B): The extent of accumulation after repeat dosing will be determined based on the observed Cmax accumulation,  $R_o$ . An assessment of time to achieve steady state will be made based on visual inspection of the trough concentrations by day. Dose proportionality may be assessed using similar methods to the single dose.

Impact of Grapefruit Juice (Part C) Log transformed AUC(0-∞) [or if not available AUC(0-t) or AUC (0-t')] for periods 3 and 4 will be analysed using a mixed model with fixed regimen and period effects and random subject effect. Between regimen differences will be computed and back transformed to provide point estimates and 90% CI for the ratio of AUC for GSK3915393 PO with GFJ: GSK3915393 PO + water, and an estimate of  $F_G$  defined as the ratio of AUC GSK3915393 PO with water: GSK3915393 PO + GFJ. Similar analysis will be conducted for log transformed Cmax to provide an estimate of the ratio of Cmax for GSK3915393 PO with GFJ: GSK3915393 PO + water.

Impact of itraconazole (Part C): Log transformed AUC(0-∞) [or if not available AUC(0-t) or AUC (0-t')] will be analysed for periods 1 and 2 utilising a mixed model with regimen fixed effect and subject random effect. Between regimen differences will be computed and back transformed to provide point estimates and 90% CI for the ratios of AUC for GSK3915393 IV + ITZ: GSK3915393 IV: A similar mixed model analysis utilizing period 3-5 data will be conducted to provide point estimates and 90% CI for ratio of AUC for GSK3915393 PO + ITZ: GSK3915393 PO + water. These analyses will also be conducted for log transformed Cmax to derive point estimates and 90% CI for the Cmax ratios of interest.

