4.5. Changes to Protocol Defined Analyses

N/A

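### Would the Part C fallback to AUC(0-τ) cut the itraconazole profiles short and understate the interaction ratios?

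*SAP*

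**What the plan says.** In Part C the AUC for each interaction ratio is AUC(0-∞), with substitutes in a bracket. For itraconazole, SAP 4.3.6.2 has "or if not available AUC(0-t) or AUC (0-τ)] will be analysed for periods 1 and 2 utilising a mixed model". For grapefruit juice, SAP 4.3.5.2 has "or if not available AUC(0-t) or AUC (0-τ)] for periods 3 and 4 will be analysed". SAP 4.3.5.1, SAP 4.3.6.1 and footnote 1 of SAP Table 3 (the F_G calculation) carry the same two substitutes.

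SAP 1.1.1 describes AUC(0-τ) as the area over the dosing interval, among the Part B endpoints. Table 3 gives the Part B intervals as 0-10 h after the first daily dose and 10-24 h after the second. SAP 4.3.3.2 c models AUC(0-τ) after the first dose to "obtain point and 90% CI estimates for Ro for each active dose", and Table 3 defines that ratio on AUC(0-10), so τ is 10 h there. The Part C block of Table 3 has rows for AUC(0-t) and AUC(0-∞) and none for AUC(0-τ).

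Protocol 9.4.2 has a different symbol at the matching place: "or if not available AUC(0-t) or AUC (0-t')] will be analysed for periods 1 and 2". It does not define t'. For Part A the SAP names a single substitute: "or AUC(0-t) if AUC (0- ∞) cannot be derived] and Cmax will be displayed graphically versus dose". SAP 4.5, headed "Changes to Protocol Defined Analyses", reads N/A.

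Protocol 1.3.3 samples Period 1 (IV alone) to 10 h, Period 2 (IV with itraconazole) to 60 h, Periods 3 and 4 (oral) to 24 h and Period 5 (oral with itraconazole) to 60 h.

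**The concern.** A dosing-interval area has no meaning after a single dose. The only first-dose value of τ in the SAP is 10 h, which is also the last sampling time for IV dosing alone, so it could look like a natural common horizon. Protocol 4.2 expects that itraconazole may lengthen the half-life considerably, and sampling to 60 h is there to catch the tail. An area stopped at 10 h would lose part of that tail in the itraconazole period and little in the reference period, so the ratio would be too small. These ratios are summary measures for the primary Part C objectives in SAP Table 2. The SAP sets no order between the two substitutes, does not say that both regimens in a ratio use the same one, and does not record the departure from the protocol's symbol.

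**Working it through.** **1. The plan's own figure.** Protocol 9.2 and SAP 5 give 90% CI limits of 0.78 and 1.28 times the ratio, with 12 subjects and a within-subject CV of 35%. Here s = √ln(1 + 0.35²) = 0.340 and t(0.95, 11 df) = 1.796. The half-width is 1.796 × 0.340 × √(2/12) = 0.249, and exp(∓0.249) = 0.779 and 1.283. The figure reproduces. It does not depend on which AUC is used and serves below as a yardstick.

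**2. Model for the truncation.** Assume one compartment, a 1 h infusion, itraconazole lowering clearance only (so half-life rises by the true ratio R), and an assay limit that does not bind. The share of AUC(0-∞) collected by time T is

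f(T) = 1 − [(1 − e^−k)/k] · e^−k(T−1), with k = ln 2 / half-life.

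The reference half-lives are 2 h (upper end of the prediction in protocol 4.3.1), 1 h (protocol 4.3.5: ln 2 × 106/72.2 = 1.02 h) and 0.4 h (step 4). R = 2.5, 5 and 10 are scenarios from protocol Table 5. The ratio seen on 0-10 h is R × f(10, itraconazole)/f(10, reference). On AUC(0-t) it is R × f(60, itraconazole)/f(10, reference).

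| Reference half-life | R | Half-life with itraconazole | Share beyond 60 h | Ratio on 0-10 h | Ratio on AUC(0-t) |
|---|---|---|---|---|---|
| 0.4 h | 2.5 | 1 h | 0.0% | 2.50 | 2.50 |
| 0.4 h | 5 | 2 h | 0.0% | 4.81 | 5.00 |
| 0.4 h | 10 | 4 h | 0.0% | 8.07 | 10.00 |
| 1 h | 2.5 | 2.5 h | 0.0% | 2.32 | 2.50 |
| 1 h | 5 | 5 h | 0.0% | 3.66 | 5.01 |
| 1 h | 10 | 10 h | 1.6% | 4.83 | 9.85 |
| 2 h | 2.5 | 5 h | 0.0% | 1.90 | 2.60 |
| 2 h | 5 | 10 h | 1.6% | 2.50 | 5.11 |
| 2 h | 10 | 20 h | 12.7% | 2.91 | 9.07 |

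So a 10 h cut could matter: in several rows the ratio falls by more than the factor 0.78.

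**3. Would the substitute be used?** Only if AUC(0-∞) is unavailable. The Part A row of SAP Table 3 flags AUC(0-∞) above 20% extrapolation and excludes it from summaries above 30%; Part C repeats the formula without the limits. If the same limits apply (an assumption), the worst row extrapolates 12.7%. The worst reference arm (2 h half-life, sampled to 10 h) extrapolates 1 − 0.963 = 3.7%. AUC(0-∞) is reportable in all nine rows, so the 0-10 h column describes an analysis that would not be run.

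Protocol Table 5 also lists R = 20. With a 0.4 h reference, half-life becomes 8 h and 0.6% is extrapolated. With 1 h it becomes 20 h and 12.7%. With 2 h it becomes 40 h and 35.7%, and only there does the rule fail.

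**4. Which rows fit the data?** Protocol 4.3.9 reports Part A IV means of about 5 ng/mL for Cmax and 5 ng.h/mL for AUC. In this model AUC/Cmax = 1/(1 − e^−k), which is 2.0 h at a half-life of 1 h and 3.4 h at 2 h. The observed value is about 1 h, and at most 5.5/4.5 = 1.22 h allowing for rounding, which corresponds to a half-life of 0.41 h. Only the 0.4 h rows agree. Their factors on 0-10 h are 1.00, 0.96 and 0.81, all above 0.78.

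**5. Grapefruit juice.** With the absorption rate of 2 per hour from protocol 4.3.1 and a 2 h half-life, 0-10 h holds 96.2% of the oral area. If juice acts on the gut only, as the SAP assumes, both regimens lose a similar small share, and F_G barely moves.

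**6. The symbols side by side.** The protocol writes its dosing-interval area with τ in Section 3 and with T in 9.4.2, and uses t' only in the fallback. SAP 4.3.3.1 lists AUC(0-t) for Part B where 4.3.3.2 c models AUC(0-τ). Apart from the symbol, the SAP's Part C paragraphs follow protocol 9.4.2 closely. That looks more like notation drifting between documents than a new analysis.

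**The case for a change.** The case for editing is that the ratios serve primary objectives, Part C is open label, and a choice between unordered substitutes could be made after the data are seen. The SAP also treats one protocol term in two ways, dropping it in Part A and replacing it in Part C, while SAP 4.5 declares nothing. Removing the symbol would cost only a few words.

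The textual part stands: τ is undefined in Part C, t' is undefined in the protocol, and N/A in SAP 4.5 is not strictly accurate.

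The step to biased ratios does not stand. It needs AUC(0-∞) to be unavailable, AUC(0-t) to be passed over although it is named before AUC(0-τ), and a Part B interval to be imported into a single-dose part. Nor is the protocol's term clearly safer. If t' means a common time point, it could not exceed 10 h for Period 1 against Period 2, because Period 1 sampling ends there. As for mixed types, the bracket reads most naturally as picking one variable for the whole comparison. AUC(0-t) is already a listed Part C endpoint with its own summaries, so the data to 60 h stay visible, and a supportive AUC(0-t) model would be optional.

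**Conclusion.** The concern does not call for a change. AUC(0-τ) in Part C is a last-listed symbol without a definition, most likely a slip for the protocol's t'. An analyst following the SAP in order uses AUC(0-∞), then AUC(0-t). In the nine illustrated cases AUC(0-∞) is available throughout, and AUC(0-t) would return between 0.91 and 1.04 times the true ratio.

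This rests on one-compartment kinetics, an assay limit that does not bind, and the Part A extrapolation limits carrying over to Part C. The documents give no assay limit and no half-life under itraconazole, so how often AUC(0-∞) might fail in individual participants is unknown. A true ratio of 20 with a 2 h reference half-life would breach the 30% limit, and AUC(0-t) would then give about 13.4 instead of 20. That loss comes from sampling that ends at 60 h, not from τ, and a 2 h half-life does not fit the Part A IV means in this model.
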